## ELIGIBILITY

### 7.1. Population

Participants (n=50) will be recruited from the HF clinic at Rhode Island Hospital (RIH), located in Providence, RI as well as among community dwelling adults in the Providence area.

Vulnerable populations. This study will not recruit individuals from vulnerable populations (i.e.: adults unable to consent, Infants, children, teenagers or pregnant women). Subjects with severe cognitive impairment (and thus, unable to provide informed consent) are excluded from participation in the study (see 9.2 for details).

### 7.2. Inclusion Criteria

Participants must meet all of the following inclusion criteria to participate in this study (see sections 9.1 and 9.2 for a description of the screening visit and of the screening assessments):

- Age >18
- Fluency in English language
- A diagnosis of HF (based on medical record or confirmation from participant's physician)
- Access to a telephone
- Ability to understand and speak English

### 7.3. Exclusion Criteria

Participants must meet all of the following exclusion criteria to participate in this study:

- Unwillingness/inability to provide informed consent
- New York Heart Association (NYHA) class IV heart failure or clinically unstable
- Severe hearing impairment not allowing phone delivery
- Severe depressive symptoms (defined as Hospital Anxiety and Depression Scale [HADS] depression subscale scores >14)
- Acute psychosis (from medical record)
- Severe cognitive impairment (BOMC scores > 10)
- Unable to obtain confirmation of HF diagnosis
- Recent hospitalization (< 6 weeks)

- Current (at least once a month) mind/body practice (i.e., mindfulness meditation, yoga, or tai chi)

## 8

## ENROLLMENT

### 8.1. Participants' Recruitment

Recruitment approaches will include the following:

- 1) The recruitment research assistant will identify patients scheduled for a visit at the Heart Failure Clinic at RIH (a HIPAA waiver and HIPAA preparatory to research requests are attached to this application). Patients will receive an invitation letter signed by the PI and [name] and a copy of the consent form either in person after their visit or by mail. The invitation letter will not contain any PHI nor personal identification. This package will be sent from the CBPM and mailed by study staff.
- 2) Flyers placed in clinics and in local public venues (e.g., community centers, libraries, supermarkets)
- 3) Social media (e.g. Facebook and Twitter) and on-line resources (hospital intranet; Craig's List)
- 4) Lifespan physician referrals
- 5) For items 2 & 3 physician clearance will be needed to confirm a medical diagnosis of Heart failure per study inclusion criteria.

All study recruitment materials will be submitted to IRB for approval.

We will track returns from the different recruitment venues in order to identify the most efficient recruitment strategies for the future RCT.

### 8.2. Screening and Consenting Procedures

Interest assessment phone call: Initial contact will be made via telephone by interested individuals using a dedicated phone number that will be included in the invitation letter and all recruitment materials. Individuals calling about the study will be screened by the study RA in a phone conversation to determine initial eligibility. The RA will briefly describe the study and its requirements and enquire whether the caller is still interested. The RA will explain the need to collect some information from the caller to determine whether they are eligible to participate and request verbal permission to proceed. A script and screening instrument will be used to standardize this phase of enrollment. Upon obtaining verbal consent the RA will complete the phone screen. A standardized formula will guide the RA to determine whether the caller is (a) eligible, (b) potentially eligible-pending or (c) not eligible. If the caller has been recruited via options 2 and 3, the RA will request contact information for the participant's physician and obtain verbal permission to send the participant's physician a letter to obtain a confirmation of heart failure diagnosis. Once the confirmation is received, the RA will contact the individual to schedule a screening orientation session. If the physician does not confirm a diagnosis of heart failure, the individual will be called and notified that they are not eligible for the study. Patients signaling interest will be invited for a screening visit.

Screening visit: Once the potential participant has confirmed interest in participating, he/she will receive a consent form to read discussing the purpose of the study, its risks and benefits and clearly stating that he/she can withdraw at any time without any adverse consequences. *This study will involve only ONE informed consent process.* Full informed consent will be obtained in

person by the RA in a private room at the CBPM after a thorough explanation of the study design, of the study intervention, and of the risks and benefits involved. Since the study requires access to protected health information (PHI), HIPAA authorization will be required from each individual in order to access his or her medical records. Signed informed consent forms will be kept in locked filing cabinets separate from all data. Participants will receive a copy of the consent for their records. *Once informed consent procedures are completed*, participants will undergo a battery of screening assessments (described in section 9.2). The RA will complete a screening log checking that all eligibility criteria are met at this point.

Screening failures: Microsoft ACCESS© will be used for tracking all participants who expressed interest in participating and were screened for eligibility. We will collect data from all individuals assessed for eligibility (i.e., individuals who consented but then resulted non-eligible at the completion of the screening process) so that we can provide a complete Consort diagram and description of the recruitment process both for publication purposes and as an indicator of future generalizability of the study. We estimate that our screen failure rates will be ~30%, and that 70% of screened participants will be eligible for this study.

Screening window. We anticipate that the time between the completion of all screening procedures and the beginning of the intervention will not exceed 4 weeks. In case > 4 weeks have lapsed, patients will be re-contacted and re-assessed for eligibility.

Randomization. n/a. This is a pre-post design study. NO randomization is involved.

### **8.3. Retention plan**

Patients will be asked to provide two different telephone numbers (home and mobile phone number) and an email address. The study tracking system will identify participants due for a visit. We will send mail/email reminders or phone messages to remind patients of their follow-up appointments or class sessions. We will also maintain contact by sending birthday and holiday cards. Participants who wish to drop out of the study will be queried as to their reasons for doing so and every attempt will be made to address their concerns. To encourage compliance with assessment visits, we will provide a \$ 50 incentive at each visit (baseline, end of intervention, and 6 months - \$150 total). *No incentive* will be provided for participation in intervention sessions, as this might bias attendance and threaten the validity of our findings.

## **9**

## **STUDY DESIGN AND PROCEDURES**

### **9.1. Study Outcomes**

#### Primary outcomes:

- 1) Feasibility. Key feasibility metrics will include the number of screened, eligible, consented and randomized participants; retention rates; session attendance; and individual mindfulness practice.
- 2) Acceptability will be assessed using a satisfaction survey.

### Secondary outcomes:

- 1) Pre/post intervention change in self-reported and objectively assessed medication adherence and functional capacity (a clinical marker of medication adherence). Hypothesis: we will observe significant pre-post intervention improvements in medication adherence and functional capacity.
- 2) Changes in memory and attention change over time and associations between changes in memory and attention and changes in medication adherence. The goal is to explore potential mediating effects that will be formally tested in a future fully powered RCT. We hypothesize that MT will improve working memory, and that such changes will in turn be associated with improvements in adherence. Although measures of memory and attention are our primary posited mediators, we will also explore the role of mindfulness and depressive symptoms (additional potential mediators of MT effect).

## **9.2. Design Overview**

This is a pilot study use a pre-test/post-test design. The overall duration of this study will be 2 years; each individual (n=50) will be involved for 6 months. Assessments will be conducted at baseline, end of treatment, and 6- months after baseline.

## **9.3. Study Intervention**

Intervention setting. Intervention sessions will be individually delivered over the phone. Prior to the beginning of the intervention instructors will contact participants to set up the best time to deliver the intervention.

Session frequency. Participants will receive a 30-minute phone call session once a week for 8 weeks.

Mindfulness training (MT). The intervention protocol is based on the MT protocol pilot-tested in our preliminary work (see Appendix 1 for a script of each session). This intervention maintains the basic components of Mindfulness Based Stress Reduction (MBSR) but has been streamlined to distill the active ingredients for phone delivery. The MT intervention involves training in the following practices: (1) Awareness of breath, a technique in which trainees learn to attend to the sensations associated with breathing; and (2) Body scan, a technique based on the cultivation of attention to bodily sensations that would normally go unnoticed. Later, participants are gradually trained to (3) direct their attention to simple activities of daily life and (4) to become aware of their own thoughts and emotions. Only at the final session they (5) practice “open awareness” – a technique by which the participant is invited to direct his/her attention to any event arising in their field of experience at a given moment, whatever it may be, e.g., a physical sensation, sound, emotion, or thought.

**Table 2. Session by Session Overview of the MT Intervention Components**

	Session 1	Session 2	Session 3	Session 4	Session 5	Session 6	Session 7	Session 8
Awareness of breath	X	X	X	X	X	X	X	X
Body scan			X	X	X	X	X	X

Awareness of daily experience exercise		X						
Informal practice exercise				X				
Awareness of sounds exercise					X			X
Awareness of emotions exercise						X		X
Awareness of thoughts exercise							X	X
Open awareness								X

Individual home practice. In addition to the weekly training session, participants will practice mindfulness techniques for 20 minutes daily on their own with the guidance of a digitally recorded, standardized guided mindfulness practice containing the techniques learned with the instructor. The mindfulness practice digital recording will be provided in different formats (CD or MP3 file) depending on the participant's preference; CD players will be offered to participants who do not possess one and MP3 versions will be uploaded onto the patient's smartphone or other device. (Please see Appendix for a script of the CD/MP3 recording).

MT instructors. The MT instructors ([name], [name], [name]) will be graduates of the teachers' training program at the University of Massachusetts Center for Mindfulness with  $\geq 5$  years teaching experience who have already participated in studies involving phone-delivered MT. To ensure consistency of delivery, each patient will be trained by the same instructor throughout the intervention. Instructor will receive one 2-hour long training session (review of MT protocol. Fidelity procedures).

#### **9.4. Concomitant Interventions**

Allowed Interventions: Participants are allowed to continue ALL the medications and follow all behavioral recommendations prescribed by their care providers (i.e. dietary recommendations).

Prohibited Interventions: Concurrent yoga, tai chi, or other mind-body training.

#### **9.5. Blinding**

The RA will be responsible for the day-to-day management of the study and will not be blinded to the exposure status of the participants. We note, however, that study participants will independently perform cognitive tests and enter other data via computer interface with no RA involvement. All personnel responsible for data management and analysis will be blinded to participants' exposure status.

The mindfulness instructors cannot be blinded to exposure status but will be blinded to study hypotheses.

# 10

## STUDY ASSESSMENTS

Screening, baseline and follow-up assessments will be completed in a private room located at the CBPM. The CBPM occupy 20,000 square feet of space in the Coro Building, of which 3700 for the exclusive purpose of meeting with research subjects. This area consists of conference rooms for orientations and group meetings, private assessment rooms for one-on-one appointments, and two control rooms from which an operator can monitor private observation rooms. The CORO Building has 24-hour security including security officers, a panic system to alert security, and any other emergency response system if necessary. We also have several staff certified in CPR and Basic Life Saving response. In response to the COVID-19 pandemic, and due to the fact that this is a high-risk population, follow-up assessments will now be completed over the telephone, via video-conference (using secure, HIPAA compliant videoconferencing software), or by mailing study surveys (that will be returned using pre-stamped envelopes) depending on the participant preference and internet accessibility.

The full assessment package will take approximately 45 minutes to complete. Since not all participants can be reached for assessments on their due date, windows have been established to determine when assessments are counted as missed (table 3).

**Table 3.**

Assessment	Window before	Window following
3 months	+/- 1 week	+/- 1 week
6 months	+/- 1 week	+/- 1 week

### 10.1. Study Assessments Schedule

This table diagrams the study measures and the schedule of administration.

	Screening	Baseline	At each session	3 m	6 m
Consent form	X				
HIPAA	X				
Contact information	X				
Eligibility check log	X				
Cognitive impairment (BOMC)	X				
Adherence (Voils scale part 1)		X		X	X
Depression (HADS)	X			X	X
Height, weight, hip, waist measures		X		X	X
Blood pressure		X		X	X
Demographics		X			
Medical history		X			
Medications & other therapies		X		X	X
N screened		X			
N eligible		X			

N refusing to participate		X		
Reasons for refusal		X		
Dropouts and lost to follow-up			X	X
Reason(s) for dropping out			X	X
Sessions attendance		X		
Individual MT practice		X	X	X
Program satisfaction scale			X	X
Program evaluation survey			X	
Sleep Quality (PSQI)		X	X	X
Cognitive assessment battery		X	X	X
Walking test		X	X	X
Social Support		X	X	X
Depression (HADS)		X		X
Mindfulness (MAIA)		X		X
Five Facets of Mindfulness (FFM)		X		X
Adherence (MEMS caps)		X		X
Voils Self-Reported Adherence (part 2)		X		X

MT = mindfulness training

Note: screening and baseline assessments occur at same visit

## 10.2. Screening Assessments

These evaluations occur to determine if the candidate is eligible for the study (see also 7.2).

- The Blessed Orientation Memory and Concentration test (BOMC) will be used to screen for **severe cognitive impairment**. Patients with BOMC scores  $\geq 10$  will be excluded because they lack the cognitive skills to learn the intervention.
- **Depression** will be assessed using the HADS, a self-administered questionnaire with two sub-scales (0-21) measuring anxiety and depression, with higher scores indicating greater psychological morbidity. A good correlation has been reported between the HADS and other commonly used measures of depression. Finally, the HADS has been validated in cardiac patients; since the HADS focuses on cognitive symptoms of depression instead of physical symptoms, it is particularly useful in these patients, where symptoms of the underlying cardiac disease often overlap with the physical symptoms of depression. Scores will be calculated immediately after completion. Patients with HADS scores indicating severe distress ( $> 14$ ) will be excluded from the study and referred to their primary provider – please see Human Subjects section for details.
- We note that in this version of the protocol we eliminated “suboptimal adherence” as an inclusion criterion. The reasons for this modification are as follows: 1) Even if patients report to be adherent at baseline, adherence declines over time. By including only participants who are non-adherent, we would not be capturing those that later become non-adherent. 2) This phenomenon is documented in the HF literature: adherence tends to decline even among HF patients who are initially adherent.

### 10.3. Baseline Assessments

- Medication Event Monitoring Systems (MEMS) will be used as an *objective measure of medication adherence*. MEMS caps (AARDEX USA, Inc., Union City, CA) are medication containers and caps equipped with a digital microchip recording date and time of each cap opening and are one of the most widely used objective method of adherence assessment in research settings. We will monitor ONE medication per patient using the criteria adopted by Wu et al. Briefly, if the patient takes any HF medication *twice* a day, this medication will be MEMS-monitored. If all HF medications have the same daily prescription schedule, the  $\beta$ -blocker will be monitored. If the patient does not receive a  $\beta$ -blocker, the ACE inhibitor or the angiotensin receptor blocker will be used instead. If none of these drugs is prescribed, the aldosterone antagonist or statin, or digoxin or diuretic will be monitored. Participants will receive a MEMS bottle at the baseline visit and will be instructed to open it only when they actually take their medication; they will also be trained to keep track of unscheduled lid openings (i.e. refills, accidental openings) in a diary; these events will be removed prior to analysis. After the baseline visit, participants will enter a 30-day run-in for the assessment of baseline adherence. Participants will start using the cap on the day following the baseline visit (=time 0), and the intervention will start 30 days later; this 30-day period will be considered our baseline.
- *Self-reported medication adherence* will be measured using the Voils medication adherence measure, a validated measure of adherence behaviors (part 1) as well as reasons for non-adherence (part 2). The item response category consistent with perfect adherence (i.e., “none of the time” or “never”) are assigned a value of 1, and the item response category reflecting most nonadherence is assigned a value of 5 (i.e., “all of the time” or “always”). Higher scores indicate worse adherence behaviors.
- *Cognitive measures* (selected from the NIH Toolbox Cognition module, see Appendix) will include:
  - 1) The Flanker Inhibitory Control and Attention Test. This test measures attention and inhibitory control. During the test, participants are instructed to focus on a stimulus while inhibiting attention to another stimulus (arrows). Sometimes the middle stimulus points in the same direction as the “flankers” (congruent) and sometimes in the opposite direction (incongruent) over 20 trials;
  - 2) The Oral Symbol Digit Test assesses working memory and processing speed. A key with nine abstract symbols is presented - each paired with a number between 1 and 9. Participants are asked to verbally indicate which numbers go with the symbols that are presented in a long string on the computer screen. The participant is given 120 seconds to call out as many numbers that go with the corresponding symbols as he/she can – in order, without skipping any;
  - 3) The List Sorting Working Memory Test requires working memory for the sequencing of visually and orally presented stimuli. Pictures of foods and animals are displayed with accompanying audio recording and written text (e.g., “elephant”), and the participant is asked to say the items back in size order from smallest to largest, first within a single dimension (either animals or foods) and then on two dimensions (foods, then animals).
  - 4) The Picture Sequence Memory Test is a measure of episodic memory. Sequences of pictured objects and activities are presented in a particular order. The participants are asked to reproduce the sequence of pictures that is shown on the screen. Participants respond by dragging pictures from the yellow box on the screen into the gray boxes on the screen.

5) The Dimensional Change Card Sort Test is a measure of cognitive flexibility and attention. Two target pictures are presented that vary along two dimensions (e.g., shape and color). Participants are asked to match a series of bivalent test pictures (e.g., yellow balls and blue trucks) to the target pictures, first according to one dimension (e.g., color) and then, after a number of trials, according to the other dimension (e.g., shape). The relevant dimension for sorting is indicated by a cue word (e.g., “shape” or “color”) that appears on the screen for all participants.

Performance on all these measures correlates significantly with scores on “gold standard” neuropsychological tests of each of the cognitive domains of interest and have high test-retest reliability, internal consistency, and convergent and divergent validity. Each test will be independently completed by study participants (3-5 minutes each) after a baseline practice trial using a study tablet. During phase 1 of this study we will develop a standardized protocol for the administration of cognitive tests, which will be included in the study manual of operations. The total time needed for the administration of the cognitive battery is 24 minutes.

- **Social support:** The Multidimensional Scale of Perceived Social Support is a 12-item, uni-dimensional tool to measure how one perceives their social support system, including individuals sources of social support (i.e., family, friends, and significant other).
- **Depression** will be assessed using the HADS, a self-administered questionnaire with two sub-scales (0-21) measuring anxiety and depression, with higher scores indicating greater psychological morbidity. If at any time during the study a participant scores >14 on the depression subscale, the RA will start a suicidality assessment (see suicidality protocol).
- **Mindfulness** will be assessed using the Multidimensional Assessment of Interoceptive Awareness (MAIA), a 32-item, 8-subscale self-report measure (recommended by the NIH Science of Behavior Change Research Network), with higher scores indicating higher levels of positive awareness as well as the Five Facets of Mindfulness (FFM), an instrument derived from a factor analysis of questionnaires measuring mindfulness in daily life.
- **Sleep quality** will be assessed using the Pittsburgh Sleep Quality Index (PSQI), a measure of sleep quality and quantity, based on recall of sleep behaviors in the past month. Scores coded from zero to three; the overall score range is 0-21.
- **Weight, height, waist/hip ratio** will be measured using standardized procedures (described in the study manual of operations)
- **Blood pressure** will be measured using a Dinamap XL automated BP monitor according to current recommendations.
- **Exercise capacity** will be assessed via the 6 min walking test, a simple, safe and reliable first-line assessment of functional status that correlates with peak oxygen uptake and also predicted survival in HF drug trials.
- **Socio-demographics** (age, sex, race/ethnicity, education, marital status, income, insurance status) will be self-reported using standard forms validated in other studies
- **Medical history** (coronary risk factors; *previous MI or stroke*; *other co-morbidities*): this information will be abstracted from medical records using standard abstraction forms that have been validated in previous studies

- *Medications & other therapies* information will be self-reported using a standardized form.

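### The MEMS baseline is the first 30 days of cap use, so a start-up effect of monitoring, if there is one, may bias the single-arm change in objective adherence in either direction

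*Combined protocol and SAP*

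**What the plan says.** Section 10.3 (Baseline Assessments) says that after the baseline visit "participants will enter a 30-day run-in for the assessment of baseline adherence". Cap use begins the next day, which is time 0, and "the intervention will start 30 days later; this 30-day period will be considered our baseline". The run-in is therefore the baseline measurement itself, not an adaptation period before it.

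The only cleaning rule in that section has participants "keep track of unscheduled lid openings (i.e. refills, accidental openings) in a diary; these events will be removed prior to analysis". The cap works by "recording date and time of each cap opening", so a daily series exists for every participant.

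Section 8.2 states: "This is a pre-post design study. NO randomization is involved". Section 14.3 models each secondary outcome with terms for time, the outcome's baseline value and possible confounders. It names no term for a trend within the baseline period. The MEMS summary measure and the follow-up MEMS window are not defined.

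Section 10.2, explaining why suboptimal adherence was dropped as an entry criterion, notes that "adherence tends to decline even among HF patients who are initially adherent".

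**The concern.** The pre value starts on the first day with a new monitored bottle and a diary. Those are the days on which a start-up effect would be expected, whether it is a temporary lift from being watched or faulty cap use while the routine is learned. If the effect fades, the pre value contains it and the post value largely does not. With one arm, nothing else in the design absorbs the difference.

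Aim 2 includes objectively assessed adherence and hypothesises a pre-post improvement. A fading lift could hide a real gain or make it look like a fall; early cap misuse could create or inflate one. Either error could carry into the planning of the future randomised trial. The information needed to look for the problem is already being recorded.

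**Working it through.** **1. The plan's own figure.** Section 14.4 claims 80% power with n = 50 and two-sided alpha 0.05, but gives no target change and no SD, so the figure cannot be reproduced. Back-solving a paired test: (1.960 + 0.842)/√50 = 0.396 SD by normal approximation, 0.404 SD by noncentral t. This serves below only as a yardstick.

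**2. Size of the bias if a lift exists.** From the documents: baseline is days 1-30. Assumed: lift on day d = L × 0.5^((d-1)/h), with L = 5 or 10 points and h = 7 or 14 days; 3-month window days 62-91. Bias = mean lift in the follow-up window minus mean lift in the baseline window.

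Example, L = 5 and h = 7: the daily ratio is q = 0.5^(1/7) = 0.906. The mean over days 1-30 is 5 × (1 - q^30)/(1 - q)/30 = 1.68. The mean over days 62-91 is below 0.01. The bias is -1.67.

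| L | h (days) | Mean lift, days 1-30 | Mean lift, days 16-30 | Mean lift, days 62-91 | Bias, 30-day baseline | Bias, days 16-30 |
|---|---|---|---|---|---|---|
| 5 | 7 | 1.68 | 0.62 | 0.00 | -1.67 | -0.62 |
| 5 | 14 | 2.67 | 1.72 | 0.13 | -2.54 | -1.59 |
| 10 | 7 | 3.35 | 1.24 | 0.01 | -3.35 | -1.23 |
| 10 | 14 | 5.34 | 3.44 | 0.26 | -5.08 | -3.18 |

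(Differences taken before rounding.) With half-lives of 30 to 60 days and L = 5, the 30-day bias is -2.2 to -2.8 and days 16-30 still leave -1.8 to -2.1. The companion baseline helps most when the effect fades fast.

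**3. The opposite sign.** Replace the lift by 5 points of early under-recording with h = 7. A true gain of 6 points then appears as 6 + 1.7 = 7.7 with the 30-day baseline and 6 + 0.6 = 6.6 with days 16-30. The later window reduces the bias whichever way it runs.

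**4. What such a bias does to power.** Take the true change as 0.404 SD and assume an SD of change of 15, 20 or 25 points. A 2-point downward bias leaves 0.404 - 2/SD = 0.271, 0.304 or 0.324 SD, and power of 47%, 56% or 61%. A 5-point bias leaves 8%, 19% or 29%.

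**5. What the companion analysis costs.** Illustrative simulation: 50 people, once-daily drug, person means Beta(6,2) (mean 75%), person drift SD 8 points from day 61, and a 6-point gain from day 31. The mean change without a lift was 5.3 points; the SE was 1.40 (30 days) and 1.75 (days 16-30), a ratio of 1.25. Power ≈ Φ(change/SE - 1.96), using the simulated biases, which are close to those in step 2:

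| Lift, half-life | Change, 30-day | Power | Change, days 16-30 | Power |
|---|---|---|---|---|
| none | 5.3 | 97% | 5.3 | 86% |
| 5, 7 d | 5.3 - 1.6 = 3.7 | 75% | 5.3 - 0.6 = 4.7 | 77% |
| 5, 14 d | 5.3 - 2.5 = 2.8 | 52% | 5.3 - 1.6 = 3.7 | 56% |
| 10, 7 d | 5.3 - 3.2 = 2.1 | 32% | 5.3 - 1.3 = 4.0 | 63% |
| 10, 14 d | 5.3 - 4.7 = 0.6 | 6% | 5.3 - 3.0 = 2.3 | 26% |

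**6. Natural decline is a different matter.** Suppose adherence falls steadily by 1 point per 30 days (assumed). Between window centres, the 30-day baseline gives (76.5 - 15.5)/30 = 2.03 points of decline at 3 months; days 16-30 give (76.5 - 23)/30 = 1.78. The later window barely corrects it.

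**7. Limits of daily modelling in one arm.** Extrapolating a straight line from days 1-30 to a 30-day window centred at day m multiplies the SE by √[(1/30 + 1/30 + (m - 15.5)²/2247.5)/(1/30 + 1/30)]. That is 5.1 at m = 76.5 and 12.3 at m = 165.5, with independent daily errors.

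A model with a before/after step plus log(days since cap start) avoids that inflation but fails otherwise. Fitted to noiseless days 1-180 with no lift and a 6-point gain building linearly over the eight weekly sessions (days 31-86), its step term returns 0.55 points. The plain comparison returns 4.9 points (days 31-180) or 6.0 (last 30 days). With a 5-point lift and 14-day half-life it returns -0.3, against 2.4 for the plain comparison over days 31-180. The log term absorbs the intervention effect.

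**The case against.** The strongest reply is that the documents nowhere say monitoring lifts adherence, that a lift peaks in these 30 days, or that it fades. That stands. A reader might infer that the objective outcome is biased downward; the documents support only that it may be biased, in a direction they do not fix.

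A reader might also take the remark on decline in section 10.2 as support. It describes natural decline in heart failure patients, not reactivity to a cap, and step 6 shows that a later baseline window does little about it. Nor does section 14.3 describe the MEMS comparison closely enough to say that a fall during the run-in would certainly be counted as the intervention's result.

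A further tempting reading is that time-stamped data could separate the start-up effect from the intervention. They can show a trend within days 1-30. An effect still fading after day 30 overlaps the sessions and, without a control arm, is separated only by assuming its shape.

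Finally, replacing the 30-day baseline outright is a debatable trade: with no lift it costs about 11 points of power (97% to 86%), and at a 5-point lift it gains only 2 to 4. This stands against substitution, but not against a companion analysis.

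**Conclusion.** The point holds as a conditional risk. The first 30 days of cap use are the whole MEMS baseline, with no adaptation days, no control arm and no stated pre-intervention trend term, so any wear-in effect that fades enters the pre-post change. On an assumed day-1 lift of 5 to 10 points and a half-life of 7 to 14 days, the bias at 3 months is about -1.7 to -5 points; early cap misuse would give a bias of the opposite sign. These sizes rest entirely on the assumed lift, decay and follow-up window.

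Using days 16-30 cuts the bias to about -0.6 to -3.2 points in the same scenarios: a reduction, not a cure. The matter affects the interpretation of a secondary outcome in a feasibility pilot and leaves the feasibility and acceptability outcomes untouched.

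**What to change.** Keep the 30-day MEMS baseline as planned. Add to section 14.3, before analysis:

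- a companion analysis of MEMS change with days 16-30 as the baseline, treating days 1-15 as adaptation to the cap;
- a plot or test of the daily adherence trend within days 1-30;
- a reporting rule: if the two baselines give materially different changes, or there is a trend within the run-in, that part of the change is not attributed to mindfulness training, and the objective result is reported as open to monitoring reactivity and natural decline.

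Do not rely on a model with a log(days since cap start) term, for the reason in step 7.

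The cost is a few lines of analysis text and no new data. The companion estimate is less precise, with a standard error about 25% larger under the assumptions of step 5, which is why it should stand beside the 30-day result and not replace it. The day-15 split is a choice of convenience that the documents do not dictate, so it should be fixed in advance.
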